As adolescents mature along different trajectories, we plan open-ended questions to ask about intention, experiences (self/referents), and contraceptive qualities. Given that many in our ED reported relationship abuse, we will use a trauma-informed approach (i.e., realize, recognize, respond, resist re-traumatization) to foster collaboration, explore safety, and offer harm reduction strategies.⁴⁸⁻⁴⁹ We will help participants 1) map information onto values and lifestyle, and 2) anticipate and solve problems, including identification of a trusted adult. We will address risk misperceptions use visual aids, and counsel dual protection with condoms. Based on our work and others, providers will provide 10-15 minutes for counseling; this is easily integrated into most ED visits. Counseling sessions will occur after patients have completed triaging, without interrupting the evaluation of standard of care services.

Providers will also have access to educational material, which can be distributed to adolescents randomized in MLI arm. These documents include the following: FDA Approved factsheets (Ring, Pill, Patch, Mini Pill, Progestin IUD, Implant, Non-Hormonal Gel, Emergency Contraception, and Depo), Switching Birth

SHORT TITLE: Reducing Pregnancy in the ED

Control, IUD Facts, Implant Facts, Contraception Choices, and CMH Clinic Hours and Locations. The contraception handouts that are being provided will help to provide further clarifications regarding medication effectiveness, adherence instructions, as well as medication side effects.

C6eii. Adolescent Randomization and Treatment: Randomization will be in a 1:1 ratio. Due to potential influence of previous contraception use on uptake, we will use block randomization with randomly selected blocks of 4 or 8 to balance allocation of those with previous use equally between arms.⁴⁸ [name] will create the master randomization list for both Children's Mercy and Children's Hospital of Philadelphia, placing each assignment in a sealed envelope numbered sequentially from 001.⁵⁴ Participant IDs will be assigned beginning with 001. After consent, a research assistant will open the corresponding envelope to carry out the arm assignment, notifying the providers before counseling is completed.

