Prior to adolescent patients being enrolled, providers will be enrolled to participate in the study. Providers will be trained on motivational interviewing practices, contraception methods, as well as medication ordering practices.

Research team staff will screen potential study candidates via electronic tracking board. The research team will approach patients to ensure that they meet qualifications for the study. If qualifications are meet, the research team will provide consent/assent to the patient, conduct a pre-counseling survey, then notify a study provider of study status. Once the subject has been enrolled, the study provider will provide contraception counseling, while incorporating motivational interviewing techniques. Counseling sessions will be audio recorded and analyzed periodically for fidelity. At the completion of counseling, the study provider will offer the participant various contraception options and incorporate warm-referral practices to encourage follow-up at a local health clinic. The subject and provider will complete the Adolescent Post-Counseling Survey via REDCap at the end of their initial enrollment .

Immediately after the initial enrollment and at thirty-days post intervention, the research team staff will conduct a medical chart review. At thirty days, three months and six months post-intervention, a follow-up survey will be sent to the participant. OOP and provider staff will participate in semi-structured interviews that can be completed either in-person, virtually, or via telephone at 6-months to evaluate the feasibility of the study.

6.2

To help ensure the safety and validity of this study, we will ensure that provider staff are properly trained prior to enrollment. Training sessions will cover interviewing techniques, contraception, and ordering practices.

Members of the study team will also review audio recordings periodically for intervention fidelity.

6.3

Prior to approaching an adolescent participant, research team members will view the medical chart to ensure eligibility. Team members will look for the following, date of birth, custody status, and current contraception usage. In the post-intervention medical chart review, team members will look to see if a follow-up visit had been completed, and if so, if any services were obtained.

Surveys from adolescent participants will assess attitudes towards contraception, pregnancy prevention methods, perceived risk of contraception, and barriers to follow-up care.

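### The protocol credits blocks of 4 or 8 with balancing previous contraceptive users between arms, but describes no strata; as written, blocking equalises arm sizes and does not control previous use (minor).

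*Protocol*

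**What the plan says.** Protocol 6.0 (C6eii) sets 1:1 allocation. It gives the possible effect of earlier contraceptive use on uptake as the reason for its method: "we will use block randomization with randomly selected blocks of 4 or 8 to balance allocation of those with previous use equally between arms".

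The procedure follows in three steps. One person "will create the master randomization list for both" hospitals, "placing each assignment in a sealed envelope numbered sequentially from 001". Then "Participant IDs will be assigned beginning with 001". Finally, "After consent, a research assistant will open the corresponding envelope to carry out the arm assignment".

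On when previous use might be known, the Protocol 6.0 workflow has staff obtain consent or assent, "conduct a pre-counseling survey, then notify a study provider of study status". Protocol 6.3 describes the chart check before approach: "Team members will look for the following, date of birth, custody status, and current contraception usage". It also says: "Surveys from adolescent participants will assess attitudes towards contraception, pregnancy prevention methods".

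The SAP compares day-30 contraceptive use between arms by intention to treat with Fisher's exact test. It says that effect sizes are examined alongside P values. It names no stratification or adjustment.

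**The concern.** Permuted blocks force near-equal arm totals within whatever list they are applied to. They balance a covariate only if each level of that covariate has its own list. The protocol claims balance on previous use, yet it names no strata, no separate envelope series, and no step in which previous-use status decides which envelope is opened. An envelope matched to a sequential ID fits an unstratified list.

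If the procedure was followed as written, the trial lacks a property that the protocol says it has, on a factor that the protocol itself singles out. A reader of the results might then take balance on previous use as built in and not look for it. The analysis does not make up for this, because the only day-30 test named is unadjusted.

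**Working it through.** **Inputs from the documents.** N = 98, 49 per hospital (Protocol 1.0); 1:1 allocation; blocks of 4 or 8 chosen at random (Protocol 6.0). The documents give no figure for balance, so there is none to reproduce.

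**Assumed inputs.** The documents give neither the share of previous users (q) nor its effect on initiation (d). I take q = 30-50%, d = 15-25 points, and day-30 rates of 30% and 50%.

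**Step 1: imbalance in the proportion of previous users.** With 49 per arm and no strata, SD = 100 × √(2q(1−q)/49). At q = 0.3 this is 100 × √(0.42/49) = 9.26 points. Simulation, 10,000 trials per setting, SD in points:

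| q | Formula | One blocked list | Simple randomisation | Lists by previous use | Lists by site × previous use |
|---|---|---|---|---|---|
| 30% | 9.26 | 9.2-9.4 | 9.3 | 1.75-1.77 | 2.50 |
| 40% | 9.90 | 9.94 | 9.92 | 1.67 | 2.36 |
| 50% | 10.10 | 9.9-10.2 | 10.2-10.3 | 1.64-1.65 | 2.32-2.35 |

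On proportions, a single blocked list does no better than simple randomisation.

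**Step 2: the same question in counts.** Chance that the arms differ by 6 or more previous users (20,000 trials per setting):

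| q | Simple randomisation | One blocked list | Separate lists by site only | Lists by site × previous use |
|---|---|---|---|---|
| 30% | 31% | 22% | 22% | about 0.1% or less |
| 50% | 43% | 27% | 27% | about 0.1% or less |

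Blocking helps with counts, but only because it equalises arm sizes. Whether the hospitals share one envelope series makes almost no difference.

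**Step 3: cost to the day-30 estimate.** The variance of the unadjusted difference is (0.30 × 0.70 + 0.50 × 0.50)/49 = 0.46/49, so its SD is 9.69 points. The share due to previous use is R² = d²q(1−q) / mean within-arm variance, and ignoring it inflates the standard error by 1/√(1−R²).

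- Middle case, q = 0.4, d = 0.20: R² = 0.04 × 0.24 / 0.23 = 0.042; inflation 1.022.
- Smallest, q = 0.3, d = 0.15, rates 40% and 60%: 0.0225 × 0.21 / 0.24 = 0.020; inflation 1.010.
- Largest, q = 0.5, d = 0.25, rates 20% and 40%: 0.0625 × 0.25 / 0.20 = 0.078; inflation 1.042.

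The range is therefore 1.0-4.2%. The imbalance is already inside this standard error. In the middle case its contribution is 9.90 × 0.20 = 1.98 points, and √(9.69² − 1.98²) = 9.49, which is 9.69/1.022 up to rounding.

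**Step 4: what adjustment recovers.** One blocked list, 10,000 trials per setting, SD of the day-30 difference in points. MH is the Mantel-Haenszel risk difference, Σw(p₁−p₀)/Σw with w = n₁n₀/n in each stratum. Logistic is the standardised risk difference with previous use and site as main effects.

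| q, d | Unadjusted | MH, previous use | MH, site × previous use | Logistic |
|---|---|---|---|---|
| 0.3, 0.15 | 9.66 | 9.63 | 9.71 | 9.67 |
| 0.3, 0.25 | 9.70 | 9.44 | 9.54 | 9.50 |
| 0.4, 0.20 | 9.70 | 9.57 | 9.64 | 9.62 |
| 0.5, 0.15 | 9.76 | 9.72 | 9.81 | 9.76 |
| 0.5, 0.25 | 9.68 | 9.39 | 9.49 | 9.44 |

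These rows assume no site effect. With an assumed 15-point site effect at q = 0.4, d = 0.20, the four figures are 9.62, 9.47, 9.48 and 9.43. Mean estimates were 19.97-20.10 against a true 20.0, so there is no bias. Two-stratum MH gains 0.03-0.29 points. Four-stratum MH is a net loss when d = 0.15.

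**The case against.** The strongest reply is that the sentence is shorthand. Balancing previous users by blocking makes sense only if blocks run within previous-use groups, so strata may have been used and simply not written down. The workflow leaves room for this: a survey precedes notification of the provider, and the surveys cover pregnancy prevention methods. This stands as a possibility. The text does not settle it, because it never says that previous use is recorded before the envelope is opened, and the chart check lists only current use. On either reading the paragraph needs correcting.

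Three further objections hold and limit the point. Blocking is not useless for counts (Step 2). The SAP already says that effect sizes are examined, so the gap is only in their form, interval and adjustment. And the practical effect is small: efficacy is preliminary, and Protocol 4.0 makes feasibility primary.

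A reader might also infer that the arms were in fact imbalanced, or that the day-30 comparison is biased. The documents support neither. Any imbalance would be random, and Fisher's test remains valid without balance on previous use.

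**Conclusion.** The stated aim and the described mechanism do not match. As written, the scheme leaves the between-arm difference in previous use with an SD of about 9-10 points, where lists by previous use would give under 2. The consequence is minor: a standard error 1.0-4.2% larger, with no bias and no loss of validity. Chance imbalance is part of that standard error and should not be counted as a second cost.

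The sizes rest on an assumed 30-50% previous use, a 15-25 point effect on initiation and assumed day-30 rates. The mismatch itself rests on no assumption. It would be too strong to say that the trial was run without strata, since they may have been omitted in drafting.

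**What to change.** 1. Reconcile the randomisation paragraph in Protocol 6.0 (C6eii). If strata were used, say that blocks were generated within previous-use strata, describe the separate envelope series, and say that previous use was recorded before the envelope was opened. If not, withdraw the balance claim and report previous use by arm.
2. Keep the Fisher test. As the form of the effect size that the SAP already says it examines, add a day-30 risk difference with 95% CI adjusted for previous use. Use either two-stratum Mantel-Haenszel, or standardised logistic regression with previous use and site as main effects. Do not use four site × previous-use Mantel-Haenszel strata, which can lose precision. Label the estimate post hoc if it is added after data were seen.

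The cost is one or two sentences, one baseline table row and one extra estimate, whose gain lies between nil and about 0.3 points in SD. The SAP is written in the past tense, so new envelope series are probably no longer possible; these reporting and analysis changes still are.

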27.0 Multi-Site Research

Drs. [name] and [name] have a detailed plan for study oversite that was reviewed and approved by the NIH. Communication between study sites will take place via conference calls and emails. Regular conference calls will take place to discuss study updates, discuss any potential barriers and concerns and discuss other study logistics. Our estimated recruitment plan is detailed in the table below.

	CMH	CHOP	Total
Providers	Approximately 30	Approximately 30	60
Adolescents	49	49	98
Other personnel	15	15	30
Total	74	74	158

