## Statistical analysis plan

We used R software (R Foundation for Statistical Computing) for analyses. In keeping with guidance discouraging the use of “statistical significance” and binary hypothesis testing based on arbitrary cutoffs (e.g.,  $P < .05$ ), we examined effect sizes along with  $P$  values and include  $P$  values without describing them as “significant” or “not significant.” Consistent with this approach, we did not attempt to control the familywise error rate (probability of at least one type I error across the study), which is not defined outside of binary hypothesis testing. We summarized closed-ended feasibility outcomes using descriptive statistics. We used an intention-to-treat analysis to assess preliminary efficacy and Fisher exact tests to compare arms on the percent of participants using contraception at 30 days. Dropouts during the index visit were treated as having no subsequent contraceptive use. Differences in average change score (e.g., attitudes) between arms were tested using nonparametric permutation tests.

*Primary Outcome:* We hypothesized the intervention would be deemed feasible by stakeholders. Drawing on similar examples in the literature, we determined a priori that the intervention would be feasible if the mean score across five Likert-scale survey items was  $\geq 4$  (range 1-5).

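### The protocol does not say how one master list, with envelopes and IDs from 001, is divided between two EDs, and the SAP's between-arm tests ignore site; the cost is precision and chance shifts, not systematic bias.

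*Protocol*

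**What the plan says.** Protocol section 6.0, under C6eii:

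- "Randomization will be in a 1:1 ratio", and "we will use block randomization with randomly selected blocks of 4 or 8". The stated purpose is "to balance allocation of those with previous use equally between arms". No other balancing factor is named.
- A study team member "will create the master randomization list for both Children's Mercy and Children's Hospital of Philadelphia", "placing each assignment in a sealed envelope numbered sequentially from 001".
- "Participant IDs will be assigned beginning with 001". A research assistant opens the matching envelope after consent.

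The target is 98 adolescents, 49 per hospital (Protocol sections 1.0, 13.0 and 27.0). The protocol does not say whether the master list holds one sequence or one per site. It gives no site prefix, number range or rule for dividing the envelopes.

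Section 27.0 describes contact between the sites: "Regular conference calls will take place to discuss study updates". It neither states nor excludes that assignments are shared.

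The SAP plans "Fisher exact tests to compare arms on the percent of participants using contraception at 30 days", and permutation tests for change scores. Neither is stratified by, restricted to or adjusted for site.

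**The concern.** Two departments recruiting in parallel cannot both open a single paper series in order unless someone has decided how to divide it. The text leaves several schemes open, and they have different properties. Under some, site balance is left to chance. Under another, balance is kept but allocation concealment is weaker.

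Site could plausibly matter for 30-day contraception. Control participants can start a method only through a referral clinic. Clinicians are paid differently at the two hospitals (section 15.0), and implant consent follows each site's own practice (section 24.0). The documents give no initiation rates by site, so the strength of the effect is unknown.

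What is at stake is the between-arm comparison, which is the limited-efficacy part of the trial. The primary endpoint, a mean feasibility score, is not threatened. Because the SAP puts weight on effect sizes, avoidable noise in the estimated difference matters more here than the crossing of a threshold.

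**Working it through.** The documents give no within-site balance figure, power or significance level, so there is no stated figure to reproduce.

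**Inputs from the documents.** 1:1 allocation; blocks of 4 or 8; 98 participants, 49 per site; no site term in the analysis. **Assumed.** The two block sizes are equally likely; site rates are as shown below; the level is two-sided 0.05, used only to check the test's calibration.

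**Step 1. Within-site balance under each scheme the text allows** (simulation, 40,000 runs; the gap is the difference between arms among a site's 49).

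| Scheme | Gap within site | Other consequence |
|---|---|---|
| One sequence shared by order of arrival | mean 4.0; 5 or more in 42%; 7 or more in 23%; 95th percentile 9 (29:20) | none for concealment |
| Same list copied to both sites | at most 3 (26:23) | duplicate IDs; the leading site's assignments match the other site's next ones |
| Independent list per site | 1 in about 95%; at most 3 | none |
| Contiguous ranges, 001–049 and 050–098 | at most 3 at the first site; 5 or more in 0.9% at the second, maximum 5 | none |

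With 49 per site, a gap of 1 is the smallest possible. Chance imbalance and predictability appear in different rows: they cannot occur together.

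**Step 2. Shift in the estimate from a given split.** Suppose one site splits a:b and the other b:a. The crude difference then moves by (a − b)/49 × the gap in site rates.

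- 28:21, 20-point gap: 7/49 × 20 = 2.9 points. With a 30-point gap: 7/49 × 30 = 4.3 points.
- 29:20, 20-point gap: 9/49 × 20 = 3.7 points.

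**Step 3. Is the crude comparison biased?** With a shared sequence and no arm effect, the mean difference is about 0 for site rates of 20%/20%, 10%/40% and 20%/60%. Fisher's type I error is 0.029, 0.033 and 0.033. With a list per site and an unstratified test, it is 0.031, 0.025 and 0.020: the test becomes more conservative as the sites diverge. So ignoring site costs something even where the lists are sound.

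**Step 4. Precision.** Compare the pooled variance p̄(1 − p̄) with the average within-site variance.

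- 40%/60%: pooled 0.50 × 0.50 = 0.250; within site (0.24 + 0.24)/2 = 0.240; reduction 4%.
- 20%/40%: pooled 0.30 × 0.70 = 0.210; within site (0.16 + 0.24)/2 = 0.200; reduction 5%.
- 20%/60%: pooled 0.40 × 0.60 = 0.240; within site (0.16 + 0.24)/2 = 0.200; reduction 17%.

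The simulated SDs at 20%/60% agree: 0.0986 for the shared sequence and 0.0898 with site lists, a variance ratio of (0.0898/0.0986)² = 0.83.

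**Step 5. How much the analysis alone recovers.** If a shared sequence was used, stratifying afterwards leaves the uneven splits in place. These inflate the within-site variance by 1/(1 − d²/49²), where d is the gap. At d = 9 this is 1/(1 − 81/2401) = 1.035. On average, with an SD of d of about 5, it is about 1 + 25/2401 = 1.01. Nearly all the gain is kept.

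**Step 6. Previous use.** Blocking an unstratified list does not balance previous contraception use. If 40% are previous users (assumed), the gap between arms among them has mean 3.9 and 95th percentile 10.

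**The case against.** The strongest reply is that this is a reporting gap. A master list for both hospitals may well contain a list per site, and then neither problem arises. Sending 001–049 to one site and 050–098 to the other would remove nearly all the imbalance and fits the planned 49/49. The 42% figure belongs only to sharing by order of arrival, which the protocol does not state. The efficacy comparison is preliminary, and the crude test is valid on average. All of this stands, and it limits the point.

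Three stronger conclusions are tempting, and the documents do not support them.

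- A reader might infer that the arms are unbalanced within site. The text shows only that balance is not ensured.
- A reader might infer that the slower site's allocations are already known. That needs identical lists at both sites and staff who see the other site's assignments. Envelopes are sealed and opened after consent, and nothing says assignments are discussed on the calls. Two different lists that both start at 001 reveal nothing.
- A reader might infer that the efficacy result is biased. Step 3 shows no systematic bias from chance imbalance under a shared sequence.

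The reply does not remove the omission. Neither weaker scheme is ruled out, and the analysis ignores site under all of them.

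**Conclusion.** The point holds as an unspecified allocation procedure together with an analysis that leaves out an available and probably useful stratifier. It does not show that randomization failed.

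Under a shared sequence, the cost is chance shifts of about 3 to 4 points for a 28:21 to 29:20 split with a 20-point site gap, and a variance that using site would cut by about 4% to 17% for gaps of 20 to 40 points. If the sites have the same rate, there is no shift and no gain. All the site rates are assumptions. Under a copied list, the concern is possible predictability and duplicate IDs, whose extent the documents do not allow one to estimate. Under separate lists or contiguous ranges, what mainly remains is the unstratified analysis.

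The remedy is nearly free, so the change should be made, but it is not critical to the primary endpoint.

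**What to change.** **Protocol.** State which scheme is or was used, how envelopes and IDs are divided between the hospitals, and who can see assignments across sites. For any remaining allocations, use independent blocked lists per site, also stratified by previous contraception use, since that is the plan's stated aim. Give envelopes and IDs a site prefix.

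**SAP.** Compare 30-day contraception with a site-stratified Mantel-Haenszel risk difference with 95% CI and a site-stratified exact test. Permute change scores within site. Report arm by site. If results have already been seen, keep the Fisher comparison, add the stratified one as a sensitivity analysis, and say that it was added later.

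**Cost.** No extra patients or data, and slightly more analysis work. Changing lists mid-trial may truncate an open block. Two lists per site also loosen the 26:23 bound, because a list can stop up to 4 apart within a block of 8. For 49 patients, one list has an even count (gap at most 4) and the other an odd count (at most 3), so the site gap is at most 4 + 3 = 7. The SAP is written in the past tense, so enrolment may be complete; in that case only the analysis change and the description of the scheme apply.

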As adolescent access to affordable, confidential contraceptive care has worsened in recent years, one approach to increase access is to utilize non-traditional settings, such as Emergency Departments (EDs).⁷ The Society for Academic Medicine recognizes the ED as an “effective site for preventive care,” evidenced by organizational conferences, consensus statements, and specialized training opportunities to reduce disparities stemming from social determinants of health.⁸⁻¹¹ Adolescents make 19 million ED visits annually, commonly for non-urgent or reproductive complaints; for many, this may be their only contact with a provider.¹²⁻¹⁴ Adolescents in the ED frequently report unprotected intercourse.^{25,40} The pregnancy risk index (PRI), an estimate of pregnancy risk in the subsequent 12 months, for adolescent females in two EDs was more than three times greater than the national average.¹⁵⁻¹⁶ Lacking a primary provider was associated with higher PRI scores. While the need for reproductive care is evident,^{17,18} the majority of ED-based studies have focused on screening for sexually transmitted infections (STIs) including HIV¹⁹⁻²⁰ and a few, primarily single-site studies have reported on acceptability of hypothetical reproductive care.^{21,22-26} Among the few addressing pregnancy prevention, most focused on emergency contraception or increasing clinic referral, with mixed results.^{27,28-31} A small open trial provided counseling and clinic referral for those wanting to initiate contraception. Only 22% completed the referral and one was found to be pregnant at her first clinic visit.³² Lack of transportation was the most common reason for not completing referral. Because interventions to address multi-level barriers and

SHORT TITLE: Reducing Pregnancy in the ED

increase contraception access are sorely needed, we aim to evaluate the feasibility of a novel ED-based intervention, utilizing a mixed methods approach.

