4.0 Study Endpoints

The primary endpoint will be the determination of feasibility. Methods for establishing feasibility vary and include levels of acceptability, satisfaction, or usefulness. Drawing on similar published criteria, the intervention will be deemed feasible if the average score across all items is ≥ 3 on closed-ended survey items for adolescents, providers, and OOPs (Table 1).

Secondary endpoints will include the following:

- The completion of a referral for any contraceptive care as assessed through EMR review or follow-up phone calls.
- The initiation of contraception as assessed through EMR review or follow-up phone calls.
- Saturation of themes from qualitative interviews that have been coded and analyzed.

Hypotheses 1.1 and 1.2: To establish feasibility, we assess multiple constructs via survey items among all stakeholders (Table 1).

Hypotheses 1.2: We will determine referral completion and date for contraception initiation (Time 0) via participant contact and review of study/medical records at thirty days after the index visit.

Table 1: Mixed-Methodology Feasibility Assessment with Adolescent and Personnel Stakeholders

Construct	Source	Index Visit: Post-intervention	Time from Index Visit	Time from Initiation (Time 0)		
			30 Days*	3 mos*	6 mos*	
Acceptability - How do stakeholders react to the intervention?	Adolescent	S	S	S	S	
	Providers	S			SSI	
	Other personnel				S, SSI	
Demand - To what extent is the innovation likely to be used?	Providers				S, SSI	
	Other personnel				S, SSI	

SHORT TITLE: Reducing Pregnancy in the ED

	Study/Medical Record*				SMRR
Implementation - To what extent can the intervention be implemented as planned (including intervention fidelity)?	Providers	S			SSI
	Other personnel				S, SSI
	Study/Medical Record*	SMRR	SMRR		
Practicality - What factors make intervention delivery challenging or facilitate delivery?	Providers	S			S, SSI
	Other personnel				S, SSI
	Study/Medical Record*				SMRR
Adaptation – How does model perform in new setting?	Providers				SSI
	Study/Medical Record*				SMRR
Integration - To what extent can model be integrated within the system?	Providers				S, SSI
	Other personnel				S, SSI
Expansion - To what extent can model be expanded to provide service?	Providers				S, SSI
	Other personnel				S, SSI
	Study/Medical Record*				SMRR
Limited efficacy testing - What are rates of contraception initiation/continuation and referral completion?	Adolescent		S	S	S
	Study/Medical Record*	SMRR			SMRR

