Legend: S=Survey, SSI= Semi-Structured Interview, SMRR= Study/Medical Record Review *+=/- 10 days

*Additional assessments include proportion enrolled, drug interaction or contraindications, intervention fidelity and duration, length of stay (participants vs. non-participants), rates of contraception initiation/continuation/referral completion, cost estimates

Data Sources: Sources include: surveys (via Research Electronic Data Capture – REDCap), semi-structured interviews, medical records, and study records (i.e., recruitment logs, interview transcripts, Providers/investigator field notes) (Table 1)

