All participants receive contraceptive counseling. Per evidence-based guidelines,⁵²⁻⁵³ MLI participants can receive contraception (one injection, three-month supply of pill/patch/ring, or subdermal implant) in the ED, or prescription for another method if desired. If a patient in this group desires another method that is not being covered by the study, patient will be made aware of their responsibility to cover the cost of the medication either out of pocket, or by using their own insurance. Due to credentialing and staffing constraints, intrauterine devices will only be available at referral clinics. MLI participants who want to initiate contraception must complete a urine pregnancy test, which must be negative. MLI participants who initiate contraception will be given a take home pregnancy test that is to be completed two weeks after enrollment. eSOC participants will have the opportunity of being referred to a follow-up appointment to discuss and begin contraception. Subjects in this group will not begin contraception in the Emergency Department or given a prescription. All participants will be referred to an adolescent gynecologist, hospital-affiliated adolescent clinic, or Title X clinic for additional care and to initiate or follow-up on contraception.

MLI participants will have a “warm transfer” to follow-up on or initiate, if preferred, selected method. Warm transfers occur with the assistance of a provider scheduling the follow-up appointment. Doing this in such a way should help to minimize barriers with navigating the healthcare system. The provider will share detailed clinic information including hours of operation and contact the receiving site. We will assist with scheduling (sending multiple reminders) and transportation. eSOC participants will be given printed information on clinics.

C6eiii. Intervention Fidelity: Counseling sessions will be audio-recorded and reviewed periodically to ensure for fidelity to content and use of MI strategies using a tool adapted from our previous work and the CHOICE Project, a clinic-based intervention efficacious for increasing contraception uptake in family-planning clinics.⁵⁴⁻⁵⁵ We will provide feedback to individual APPs if mean fidelity score ≤ 3 .

SHORT TITLE: Reducing Pregnancy in the ED

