23.0 Compensation for Research-Related Injury

Provider/OOP: Research-related injury would be highly unlikely and there will be no compensation for research-related injury. If study providers feel they need to receive care, they will need to obtain it on their own.

Adolescents: Being in this study involves no more than minimal risk, therefore we do not require compensation for research-related injuries.

Economic Burden to Subjects

Training for providers will be provided free of cost and there should be no additional economic burden to study providers.

A 3-month supply of non-LARC study related medications, plus 1 etonogestril implant for adolescents in the MLI will be provided free of charge. Urine pregnancy testing will be provided free of charge if not already included in usual ED care for adolescents.

Adolescents must provide their own transportation for any medical follow-up visits that may be needed. If an adolescent decides to begin a method of contraception, follow-up care may be sought at a local Title X clinic or any medical facility preferred by the adolescent and adolescents will be responsible for any out-of-pocket expenses which may be incurred.

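### Does the Protocol's inconsistent wording on transport to follow-up visits undermine the comparison of MLI with eSOC?

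*Protocol*

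**What the plan says.** Section 6.0 of the Protocol (Adolescent Randomization and Treatment) gives MLI participants a warm transfer. A provider helps to book the follow-up appointment, passes on clinic details and contacts the receiving site. The paragraph then adds "We will assist with scheduling (sending multiple reminders) and transportation". It closes with the other arm: "eSOC participants will be given printed information on clinics".

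The Economic Burden to Subjects text, under Section 23.0, states "Adolescents must provide their own transportation for any medical follow-up visits that may be needed". Its next sentence says that "adolescents will be responsible for any out-of-pocket expenses which may be incurred".

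The Study Summary (Section 1.0) describes the warm referral as help with scheduling and does not mention transport. Section 15.0 lists no transport payment. The SAP does not mention transport.

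Section 4.0 makes this a secondary endpoint: "The completion of a referral for any contraceptive care as assessed through EMR review or follow-up phone calls". Table 1 in the same section asks, for the implementation construct, "To what extent can the intervention be implemented as planned (including intervention fidelity", and its footnote lists "rates of contraception initiation/continuation/referral completion, cost estimates" among the additional assessments.

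**The concern.** One section says the study helps with transport, and another says adolescents see to it themselves. Both are current text; the one change-log entry shown concerns payment to providers.

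The subject is not trivial for this trial. Citing an earlier open trial in which 22% completed the referral, Section 3.0 reports: "Lack of transportation was the most common reason for not completing referral". Transport help given to one arm only would therefore act on the barrier that the Protocol itself singles out, and would form part of any difference between arms in referral completion. A reader might also ask how implementation as planned can be judged, or costs estimated, for an element that the plan states in two ways.

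**Working it through.** No figure in the plan depends on this point, so the check is a comparison of texts plus one count.

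1. **Arm concerned.** The transport sentence in Section 6.0 does not name an arm. Its paragraph opens with MLI participants and ends by contrasting eSOC, so it applies to MLI.

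2. **Overlap of scope.** The Economic Burden sentence covers any follow-up visit, and the sentence after it mentions Title X clinics, which Section 6.0 lists as a referral destination. The paragraph before it singles out MLI for free medication, so that section separates the arms when it means to. The overlap is real.

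3. **Strict contradiction or loose wording?** Assisting with transport is not the same as supplying it or paying for it. The second statement sits under a heading about who bears costs. If the study helps to arrange travel and the adolescent provides or pays for it, both sentences hold, and the out-of-pocket sentence fits that reading. The Protocol does not state it, so what the help consists of remains undefined.

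4. **How much of the referral component is unclear.** Scheduling by the provider, clinic details, contact with the receiving site and reminders appear in Section 6.0 and are contradicted nowhere. Only transport is open.

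5. **Number affected.** With 98 adolescents randomized 1:1, 98 × 1/2 = 49 are in MLI.

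6. **Effect on each analysis.**
   - *Primary feasibility criterion:* a mean of survey ratings, calculated in the same way under either reading.
   - *Contraceptive use at 30 days:* the SAP compares arms as randomized with a Fisher exact test. That test is valid whether or not transport help is in the MLI package. The observed rate could still be affected, because Section 6.0 lets MLI participants start at the clinic if they prefer and makes IUDs available only there. The documents do not allow the size of this to be computed.
   - *Referral completion:* the SAP names no between-arm test. Transport help, if given, would be one component of a deliberately multi-component arm and would not bias a comparison of the two packages.

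**The case for a change.** The best case for acting is that this is a feasibility trial, so the exact content of the intervention is part of the result. If MLI shows higher referral completion, a later team needs to know whether transport help contributed. The described fidelity procedure reviews recordings of the counseling session, which would not show help given afterwards. Chart review looks for completed visits and the services obtained. No visible item records transport help as delivered. On this view the Protocol should be amended and delivery fields added for the warm transfer, the reminders and transport, tabulated by hospital.

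Part of this stands. The two sentences do need to be reconciled, and what was delivered should be described when results are reported. The rest goes further than the documents support. The warm transfer and the reminders are not contradicted, so extra fields for them answer no inconsistency. Nothing says that transport differs between hospitals, so a table by site has no stated basis. The claim that nothing is recorded cannot be established, because the survey instruments and the fidelity tool are not shown. Field notes and study records are named data sources, and the surveys are to cover barriers to follow-up care. Finally, the SAP is written in the past tense. If follow-up has closed, new data fields could not be filled, and only a description from existing records would be possible.

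**Conclusion.** The inconsistency is real but narrow: one element of the referral support for about 49 participants, which can be read consistently although the Protocol does not spell that reading out. It makes the MLI package harder to describe. It does not bias the randomized comparison, alter the sample size or make any stated figure wrong, and it touches no between-arm test of referral completion, since the SAP names none. Reconciling the two sentences is an editorial matter, and which position holds is for the sponsor to state. Study staff can report from their records what help was given without changing the design or analysis.

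This conclusion rests on two assumptions: that the comparison of interest is between the two packages as delivered, which matches the intention-to-treat approach in the SAP, and that no claim will be made about the separate contribution of transport. The possible influence on referral completion, or on contraception started at the clinic within 30 days, is unknown and is not assumed to be zero.
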